week immunization series and again two weeks after the final immunization. With the leukapheresis products, autologous dendritic cells were prepared by culture of flask-adherent monocytes for six days in serum-free medium supplemented with GM-CSF and IL-4. CD8+ T cells, purified from PBMC by negative magnetic bead selection, were cultured with autologous dendritic cells and protein antigens for 96 hours, without *in vitro* restimulation, and ELISPOT was used as a quantitative direct assessment of effector T-cell response. As shown in Figure 6, three patients had a significant increase in the number of PAP-specific IFN γ -secreting CD8+ T cells after immunization compared with pre-immunization, one patient from each dose cohort. In addition, several subjects, including the subject with the greatest magnitude ELISPOT response, were also found to have PAP-specific memory T-cell recall responses as identified by proliferating CD4+ and CD8+ T cells in a 96-hour proliferation assay following antigen-stimulation (Figure 7). Finally, several individuals experienced a prolongation in PSA doubling time over one year following treatment compared with pre-treatment. Overall the median PSA doubling time was 6.5 months in the four months pre-treatment and 8.5 months in the 4-month on-treatment period ($p = 0.033$). Long-term PAP-specific IFN γ -secreting T-cell responses were observed in several patients up to one year after immunization. In addition, one patient went on to receive booster immunizations with 100 μ g pTGV-HP at monthly intervals. As shown in Figure 8, booster immunizations were able to augment PAP-specific CD4+ and CD8+ proliferative T cells, as well as PAP epitope-specific CD8+ T cells (Figure 9) months after the initial immunization course. Taken together, these results demonstrate that pTGV-HP can elicit PAP-specific T-cell immune responses, CD8+ T-cell responses in particular, and these responses could be elicited at even the lowest dose (100 μ g) of plasmid DNA vaccine tested. In subsequent studies, we have further found that PAP-specific IFN γ responses were detectable in several individuals at multiple time points after immunization, and the presence of this persistent immunity was associated with favorable changes in PSA doubling time. These results, demonstrating immunological efficacy with the 100 μ g dose, and safety in at least one individual with ongoing immunization at that dose, form the basis of the current trial design using a similar vaccination induction schedule, but continuing with periodic (quarterly) booster immunizations.

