1. Physical examination, including vital signs, symptoms assessment, and ECOG performance score (not required if already obtained within 14 days)
2. Blood draw for serum PSA and PAP (to be obtained prior to administration of immunization/GM-CSF). May be done up to 3 days in advance of Day 1.
3. Immunization as described in sections 6 and 8 above. Specifically, subjects will receive immunizations intradermally on the deltoid area of the lateral arm (preferentially left arm) with 0.25 cc administered at each of two adjacent sites.
4. Following vaccinations, the subjects will be observed for 60 minutes for unanticipated adverse events.

D. Second, third, fifth and sixth biweekly treatment visits (days 15, 29, 57 and 71, each +/- 2 days)

1. Symptoms assessment
2. Immunization/GM-CSF and post-treatment monitoring as described above

E. Fourth immunization/GM-CSF treatment visit (day 43 +/- 2 days)

1. Physical examination, including vital signs, symptoms assessment, and ECOG performance score
2. Blood draw for CBC, chemistry panel, serum PSA and PAP (to be obtained prior to administration of immunization/GM-CSF)
3. Immunization/GM-CSF and post-treatment monitoring as described above

F. End of initial vaccination series evaluation (2 weeks after sixth vaccination, i.e. month 3 (day 85 +/- 2 days)

1. Physical examination, including vital signs, symptoms assessment, and ECOG performance score.
2. Blood draw for CBC, chemistry panel, serum PSA and PAP (to be obtained prior to administration of immunization/GM-CSF)
3. 10 ml peripheral blood (red-top tubes) for sera to evaluate antibody responses, and 100 ml peripheral blood (green-top heparinized tubes) for T-cell response evaluation
4. Immunization/GM-CSF and post-treatment monitoring as described above
5. BIOMARKER COHORT ONLY: NaF PET/CT (can be performed +/- 14 days of this 3-month immunization/GM-CSF visit). NOTE: This study is for research purposes only and will not be used for clinical response evaluation or treatment decisions. This study will be performed only at designated sites (UWCCC and JHU).

G. Day 127 (+/- 10 days) – BIOMARKER COHORT ONLY

1. Blood draw for serum PSA and PAP (does not require a clinic visit; the purpose of this draw is to provide PSA values to determine a PSA doubling time

corresponding with the 3-6 month period over which NaF PET/CT scans are obtained).

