H. Quarterly booster immunizations (every 3 months (days 169, 253, 337, 421, 505, 589, each +/- 7 days) – beginning at month 6 immunization – up to 6 total (to complete 2-year treatment course)

1. Physical examination, including vital signs, symptoms assessment, and ECOG performance score
2. Blood draw for CBC, chemistry panel, serum PSA and PAP (to be obtained prior to administration of immunization/GM-CSF)
3. Immunization/GM-CSF and post-treatment monitoring as described above
4. CT scan abdomen/pelvis and bone scan – performed prior to second quarterly booster/treatment (i.e. 6 months after first immunization/treatment), and every 6 months (every other visit) thereafter. Can be performed +/- 7 days of study visit.
5. 10 ml peripheral blood (red-top tubes) for sera to evaluate antibody responses, and 100 ml peripheral blood (green-top heparinized tubes) for T-cell response evaluation (Quarterly for 1st year following initial series, 3 time points, only)
6. BIOMARKER COHORT ONLY: Leukapheresis (~1.0 blood volume, 100 mL collection) at month 6 evaluation for T-cell response evaluation (can be performed +/- 14 days of this study visit). This leukapheresis replaces 100-ml peripheral blood requirement in 10.G.5 above for the month 6 time point. NOTE: As an alternative to leukapheresis, 200 ml peripheral blood (green-top heparinized tubes) can be collected. This is for T-cell response evaluation and immune biomarker studies.
7. BIOMARKER COHORT ONLY: NaF PET/CT (to be performed +/- 7 days of the 6-month immunization/GM-CSF visit). NOTE: This study is for research purposes only and will not be used for clinical response evaluation or treatment decisions. This study will also be performed only at designated sites (UWCCC and JHU).

I. End of Study Visit or 2-year (Day 672 +/- 7 days) Off-Study Visit

1. Physical examination, including vital signs, symptoms assessment, and ECOG performance score
2. Blood for CBC, chemistry panel, serum PSA, serum PAP
3. 10 ml peripheral blood (red-top tubes) for sera to evaluate antibody responses, and 100 ml peripheral blood (green-top heparinized tubes) for T-cell response evaluation. [Note: these specimens not required if subject off study prior to 12 month visit. However, these will continue to be drawn at quarterly intervals up to 12 months after screening/randomization in all subjects, even if off-study prior to 12 months.]

J. Follow up for Subjects Who Come Off Study Prior to 12-Month Visit

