- 3) Median progression-free survival, and PSA progression-free survival, in patients with clinical stage D0 prostate cancer, in each study arm. Progression is defined as the appearance of metastases by radiographic imaging using RECIST 1.1 criteria (appearance of a visceral lesion >

10 mm by CT or MRI, lymph node > 15 mm in short axis, or appearance of new lesions on bone scan consistent with metastatic disease), and median progression will be calculated from the date of randomization to the first evidence of metastatic disease. Progression will also be defined as the off-study date for those patients coming off-study prior to the 24-month time point to pursue other treatments, without evidence of metastasis. PSA progression is defined as a PSA value that is at least twice as large as its baseline (day 1) counterpart. PSA progression must be confirmed with a repeat PSA blood test at least two weeks later. The time to PSA progression will be defined as the interval between day 1 and the first time when a PSA value at least twice as large as the baseline value, also confirmed in the subsequent repeat PSA test, has been observed. All post-treatment PSA values have to be obtained from the same laboratory using the same assay. PSA progression-free survival times of subjects not experiencing PSA progression by the end of the follow-up period (24 months after the last patient has been randomized) will be censored. If lost-to-follow-up, the PSA progression-free survival time will be censored at the last available serum PSA measurement date. Similarly, if a patient experiences disease progression due to the appearance of metastases, PSA progression-free survival time will be censored at the date of the last available serum PSA measurement at the off-study time-point.

Laboratory endpoints:

An immune response will be defined as a PAP-specific T-cell frequency (by ELISPOT) or proliferation precursor frequency (by T-cell proliferation studies) at the completion of treatment that is at least 3-fold higher than the baseline T-cell frequency, and statistically different from media-only controls. An IgG immune response will be defined as a titratable PAP-specific IgG antibody response by ELISA, with titer of at least 1:100, detectable after immunization that was not detectable pre-immunization.

Biomarker endpoints:

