- 2) Adverse events and toxicities observed will be categorized according to the most recent version of the NCI Common Terminology Criteria for Adverse Events. Each toxicity/adverse event observed will be assigned an attribution: unrelated, unlikely, possible, probable, or definite. The number and severity of observed toxicities will be analyzed descriptively in tabular format. Ninety-five percent confidence intervals of toxicity rates will be constructed for each study arm. Fisher's exact test will be used to compare toxicity rates between the two study arms.

3) As available, both median PSA PFS (PPFS) and progression-free survival (PFS) in the pTVG-HP DNA vaccine/GM-CSF arm will be compared to their counterparts in the placebo/GM-CSF arm using quantile regression methods for censored data [74]. PPFS and PFS will be summarized in each arm using Kaplan-Meier curves. For both PPFS and PFS, univariate and multivariate Cox proportional hazards models stratified by the aforementioned stratifying factors will be used to compare the two trial arms. The multivariate Cox proportional hazards model will adjust for treatment group and age at randomization.

Biomarker endpoints:

An immune response by ELISPOT or antigen-specific proliferation that is at least 3-fold higher than the baseline T-cell frequency will be analyzed as binary data, and its response rate estimated with a 95% confidence interval for each trial arm. An IgG immune response will also be analyzed as a binary data, and its response rate estimated with a 95% confidence interval for each trial arm. The comparison of immune responses between the two trial arms will be conducted using a stratified Mantel-Haenszel test.

It will be evaluated whether the presence of specific immune responses present at baseline are associated with the development of Th1-biased immune responses after treatment and with 2-year metastasis-free survival. Specifically, in order to determine if baseline immune responses specific for PAP are predictive (or not) for these immunological and clinical endpoints, logistic regression analysis and Cox proportional hazard regression analysis will be conducted.

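### Dating PSA progression at the visit makes the planned difference in median PSA-PFS cluster near 0 or 12 weeks once medians pass about month 5 to 6

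*Combined protocol and SAP*

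**What the plan says.** - **Dating rule** (Section 13, Study Endpoints, secondary endpoint 3). Time to PSA progression is "the interval between day 1 and the first time when a PSA value at least twice as large as the baseline value", provided a later test agrees. On confirmation: "PSA progression must be confirmed with a repeat PSA blood test at least two weeks later". The event keeps the first date, so the repeat test does not refine it.
- **PSA calendar** (Section 10.C to 10.I). After Day 1, PSA is drawn at the "Fourth immunization/GM-CSF treatment visit (day 43 +/- 2 days"), at Day 85, at Day 127 in the biomarker cohort only, and then at the visits headed "Quarterly booster immunizations (every 3 months (days 169, 253, 337, 421, 505, 589, each +/- 7 days"). The last draw is on Day 672.
- **Comparison of medians** (Section 13, Statistical Analysis Plan, secondary endpoint 3). Where available, median PSA-PFS and PFS in the vaccine arm "will be compared to their counterparts in the placebo/GM-CSF arm using quantile regression methods for censored data [74"]. No interval or test method is named for this regression, and interval censoring is not mentioned.
- **Second comparison of the same endpoint** (same paragraph). Kaplan-Meier curves are planned, and stratified Cox models "will be used to compare the two trial arms".
- **Prior data** (Section 4). "Overall the median PSA doubling time was 6.5 months in the four months pre-treatment and 8.5 months" on treatment, in the single treated group of the earlier trial.

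**The concern.** A patient's PSA passes twice baseline at some moment between two draws, but the recorded time is the later draw. From Day 169 the recorded times therefore sit in narrow bands 12 weeks apart. A sample median must land in one band or another, so the difference between two medians moves in steps of about 84 days. Two arms whose true medians share one gap can show no difference. Two arms with the same true median close to a visit can appear 12 weeks apart.

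Secondary objective 3 is worded in terms of medians, so this difference is the figure that answers it. A two-month effect, the size of the change seen in the earlier trial, is smaller than one step of the grid. The PSA values that would locate the crossing more closely are collected anyway.

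**Working it through.** **Plan's own figure.** The plan states no power or precision for PSA-PFS. Its only power figure is for the primary endpoint: 0.91 for 40% versus 70%. With 53 × 0.85 = 45 per arm and a one-sided 5% test, this recomputes as 0.90 (pooled variance) or 0.91 (unpooled). It fixes the sample size used below.

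**Where medians meet the grid.** Time since Day 1 is the visit day minus 1, so the relevant visits fall at 168, 252 and 336 days. At 30.44 days per month:
- 5.5 months = 167 days, on the Day 169 visit.
- 5.7 and 7.7 months = 174 and 234 days, both inside the gap from 168 to 252. Dated late, both round up to 252, so the difference tends to 0. The lower median is so close to 168 that it often falls back there, and the difference becomes 84 days.
- 6.5 and 8.5 months = 198 and 259 days, in adjacent gaps. They round up to 252 and 336, a difference of 84 days, but 259 is close enough to 252 that 0 also occurs.

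**Simulation.** With arm as the only covariate, censored median regression reduces to the difference in Kaplan-Meier medians. From the documents: 53 per arm (28 on the first-cohort and 25 on the biomarker calendar), visit windows, and confirmation at two weeks. Assumed, because the documents do not give them: log-normal doubling times with log-SD 0.4–0.6, and PSA coefficient of variation 10–15%. A two-month true difference is 2 × 30.44 = 61 days.

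| True medians (months) | Measure | Visit-dated | Interpolated |
|---|---|---|---|
| 5.7 v 7.7 | RMSE, days | 48–55 | 24–35 |
| 5.7 v 7.7 | estimate within 21 days of 0 | 46–48% | 4–11% |
| 6.5 v 8.5 | RMSE, days | 33–48 | 25–39 |
| 5.5 v 5.5 | 60 days or more favouring vaccine | about 23% | 0–2% |
| 6.5 v 6.5 | SD, days | 9–30 | 21–34 |

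A separate, simpler model (15% attrition, log-SD 0.6, no assay noise or confirmation) shows the two clusters directly. At 6.5 versus 8.5 months, 41% of estimates lie within 2 weeks of 0, 53% within 2 weeks of +12 weeks, and almost none at 3 to 9 weeks. Assay noise and confirmation shift the split between the clusters, not their spacing.

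**Earlier medians.** Draws are 6 weeks apart up to Day 85, and up to Day 169 in the biomarker cohort. At 3.5 versus 4.5 months in the simpler model, 34% of estimates lie 3 to 9 weeks from zero, so the 12-week step is much weaker.

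**Error rate and power, two-sided 5%.** These depend on a method the plan does not name.
- Normal approximation with bootstrap standard error: type I error at 5.5 months is 9.8–14.7% visit-dated. Power at 5.7 versus 7.7 months is 0.21–0.29 visit-dated and 0.43–0.77 interpolated.
- Percentile bootstrap: type I error at 5.5 months is 3.1–4.5% visit-dated and 3.7–4.6% interpolated. Power at 5.7 versus 7.7 months is 0.43–0.74 and 0.46–0.80; at 6.0 versus 8.0 months, 0.40–0.68 and 0.41–0.75; at 6.5 versus 8.5 months, 0.36–0.66 and 0.38–0.70.

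**Rank-based comparison.** At 6.5 versus 8.5 months in the simpler model, log-rank power is 0.53 with exact times and 0.51 visit-dated.

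**The case against.** The case for leaving the plan alone has several sound parts.

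- **Testing.** A reader might infer that the planned test has an inflated error rate and loses half its power. The documents do not support that. They name no inference method, and with a percentile bootstrap the error is about 4% and power differs by no more than about 7 points. This objection stands in full.
- **Precision.** A reader might infer that visit dating always loses precision. It does not: with equal medians mid-gap, at 6.5 months, its SD is the smaller. A small SD is not always a gain, however. At 4.5 versus 6.5 months with log-SD 0.4, the SD is 8.5 days visit-dated against 20.6 interpolated, but the visit-dated estimate is pinned near 84 days, about 84 − 61 = 23 days above the truth.
- **Anchor.** The 6.5 and 8.5 months are fitted doubling times in one treated group, not PSA-PFS medians by arm, and 6.5 months is about a month past the Day 169 visit. They are a rough guide to range only.
- **Other analyses.** A reader might infer that the whole PSA-PFS comparison reflects the calendar. The stratified Cox models are barely touched, and the doubling-time endpoint already uses all same-laboratory PSA values.
- **Model.** Interpolation imputes a date, and a simulation with log-linear PSA growth favours it. This is fair as a caution on the size of the gain. The clustering itself comes from the calendar and the dating rule, not from that assumption.

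What remains is a coarse and often misleading point estimate of the quantity named in secondary objective 3.

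**Conclusion.** The point holds for the estimated difference in median PSA-PFS, when the medians fall after about month 5 to 6. There the estimate clusters near 0 or 12 weeks. Its RMSE is about 1.6 to 2 times that of the interpolated estimate at 5.7 versus 7.7 months (55/35 to 48/24), and about 1.2 to 1.3 times at 6.5 versus 8.5 months (48/39 to 33/25). Equal medians close to a visit give a spurious 60 days or more favouring vaccine in about 23% of trials.

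The sizes rest on log-normal doubling times, the stated spread and assay variation, and medians in the range suggested by the earlier trial. The point does not extend to the Cox comparison, to error control under a suitable interval method, or to the primary endpoint. It is a worthwhile, inexpensive improvement to one secondary contrast.

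**What to change.** Keep the definition of PSA progression, the confirmation rule, the visits, and the visit-dated Kaplan-Meier and Cox analyses. For the difference in median PSA-PFS:

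1. Treat the event time as interval-censored between the last PSA below twice baseline and the first confirmed PSA at or above it. As an alternative, use the log-linear crossing of twice baseline between those two draws and then apply the planned quantile regression.
2. Name the interval method: a percentile bootstrap, or the likelihood interval from the interval-censored model.
3. Report the visit-dated medians alongside.

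The cost is SAP wording, settled before unblinding, and a short program; no new data are needed. The downside is an assumption about PSA rise between adjacent draws, or a parametric form. The secondary analysis of doubling time already fits a linear regression to log PSA, so the assumption is not new to the plan. As an indication of the gain at 6.5 versus 8.5 months (log-SD 0.6, 250 simulated trials), an interval-censored log-normal model gave an SD of 4.3 weeks against 6.8 visit-dated. Part of that comes from the model matching the simulated data, since exact times with the ordinary median gave 5.5 weeks.

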A. PAP is a tumor antigen in prostate cancer and CTL are necessary to destroy prostate tissue

PAP was first identified in 1938 and was initially used as a serum marker for the detection of prostate cancer [12, 21]. PAP expression in normal and malignant prostate cells is well-documented, and is still used in immunohistochemical staining to establish a prostate origin of metastatic carcinoma [22]. The ubiquitous expression of PAP in prostate tissue makes it an appealing antigen as a potential “universal” target for immune-directed therapies of prostate cancer, unlike specific oncogenes that may or may not be expressed by a particular tumor. Moreover, it has been demonstrated that some patients with prostate cancer have preexisting antibody and T-cell responses to PAP, suggesting that tolerance to this “self” protein can be circumvented *in vivo* [23, 24]. In particular, the demonstration of Th1-like immune responses specific for PAP suggest that an immune environment permissive of an anti-tumor response can exist in patients even without immunization.

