Figure 9: PAP-derived epitope-specific cellular immune responses can be detected long-term after initial immunization. Peripheral blood mononuclear cells were obtained from an HLA-A2-expressing patient at multiple intervals following an initial 6 biweekly immunization series and 6 monthly booster immunizations 18 months later (red bars indicate timing of these immunizations). Cells were stimulated *in vitro* for 1 week with peptides and assayed for the frequency of epitope-specific T cells among CD3+CD8+ cells by HLA-A2-specific PAP peptide-specific pentamers (ProImmune, Inc.).

5. **Objectives**

A. **Primary Objectives**

1. To evaluate the 2-year metastasis-free survival of patients with non-metastatic prostate cancer (clinical stage D0) treated with a DNA vaccine encoding PAP, with GM-CSF as an adjuvant, versus patients treated with GM-CSF only.

B. **Secondary Objectives:**

1. To evaluate if immunization with a DNA vaccine encoding PAP prolongs PSA doubling time in patients with non-metastatic prostate cancer
2. To evaluate the safety and tolerability of the pTVG-HP DNA vaccine administered to patients with clinical stage D0 prostate cancer
3. To evaluate the median progression-free survival, and PSA progression-free survival, of patients with non-metastatic prostate cancer (clinical stage D0) treated with a DNA vaccine encoding PAP, with GM-CSF as an adjuvant, versus patients treated with GM-CSF only.

C. **Laboratory Objectives:**

1. To determine if immunization with a DNA vaccine encoding PAP elicits antigen-specific T-cell and/or IgG responses
2. To determine if immune monitoring of T-cell responses can be accurately and reproducibly conducted in a multi-center vaccine trial
3. To determine if the development of PAP-specific T-cell immune responses are associated with clinical responses.

D. **Exploratory Biomarker Objectives – Expanded Subject Cohort:**

1. To determine if baseline immune responses specific for PAP are predictive (or not) for the development of PAP-specific T-cells and/or are associated with 2-year metastasis-free survival in the cohort of patients who receive a DNA vaccine encoding PAP
2. To determine if antigen spread (the development of immune responses to other cancer-associated proteins) is associated with 2-year metastasis-free survival
3. To determine if Quantitative Total Bone Imaging (QTBI) by NaF PET/CT can identify bone lesions in this patient population not detected by standard bone scintigraphy

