- 1) Baseline immune responses specific for PAP (by antigen-specific T cell proliferation, cytokine release or regulatory response by tvDTH) will be evaluated in all subjects, blinded to treatment arm.
- 2) Sera obtained at baseline and at 6 months will be used to identify whether antibody responses are elicited to other prostate-associated antigens.
- 3) Quantitative Total Bone Imaging (QTBI) will be evaluated in a blinded fashion at baseline, 3 months and 6 months. QTBI parameters will include: Standardized Uptake Values (SUV): SUVmax, SUVtotal, SUVmean, SUVpeak and volume. These image data will be used:
 1. To determine whether the presence of lesions detected by NaF PET/CT at baseline is associated with early disease progression (within 1 year) by standard radiographic imaging methods (CT and bone scintigraphy)
 2. To determine whether NaF18F- PET/CT reveals different patterns of disease progression with respect to treatment arm.
 3. To determine if growth rates, and changes in growth rates, determined by NaF PET/CT are associated with PSA doubling time and changes in PSA doubling time (PSADT₀₋₂₄, PSADT₃₋₉).

Statistical Analysis Plan

Analysis populations:

Intent-to-Treat (ITT) Population: The primary population for the efficacy analysis will be the ITT population, defined as all patients who have been randomized and have received at least one dose of pTVG-HP/rhGM-CSF or rhGM-CSF treatment.

Evaluable Efficacy Population: The secondary population for the efficacy analysis will be the Evaluable Efficacy Population. The Evaluable Efficacy Population consists of all patients who have been treated according to protocol, i.e., all inclusion/exclusion criteria are satisfied, adequate compliance with treatment (having received all pTVG-HP/rhGM-CSF or rhGM-CSF treatment until a study endpoint was reached), and have completed all radiographic assessment (until a study endpoint was reached).

Safety Population: The Safety Population for assessment of safety consists of all patients who received at least one dose of pTVG-HP/rhGM-CSF or rhGM-CSF treatment.

Primary endpoint:

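### For the T-cell predictors in exploratory objective D.1, the only T-cell response rule in Section 13 has the predictor as its denominator, which pulls the association in the negative direction

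*Combined protocol and SAP*

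**What the plan says.** Section 5.D, item 1 sets the objective: "To determine if baseline immune responses specific for PAP are predictive (or not) for the development of PAP-specific T-cells", with 2-year metastasis-free survival (MFS) as the second outcome, in patients who receive the vaccine.

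Section 13, Study Endpoints, supplies the predictors: "Baseline immune responses specific for PAP (by antigen-specific T cell proliferation, cytokine release or regulatory response by tvDTH) will be evaluated in all subjects". The Laboratory endpoints paragraph there defines a T-cell immune response as a frequency "at least 3-fold higher than the baseline T-cell frequency, and statistically different from media-only controls". The Statistical Analysis Plan (Biomarker endpoints) repeats the fold rule: "An immune response by ELISPOT or antigen-specific proliferation that is at least 3-fold higher than the baseline T-cell frequency will be analyzed as binary data". Its stated uses are a response rate per arm and a between-arm comparison.

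The next paragraph plans logistic and Cox regression to see whether baseline responses are "associated with the development of Th1-biased immune responses after treatment and with 2-year metastasis-free survival". It does not define a Th1-biased response, and nothing is said about the shared baseline.

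Section 11.B.1 gives another T-cell criterion, a t test, which also compares with pre-treatment wells. The same section subtracts the no-antigen wells when computing frequencies.

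**The concern.** A patient whose baseline reads high, truly or through assay noise, needs a much larger post-treatment value to reach 3-fold. A patient whose baseline reads low needs a small one. Section 2.A reports that "some patients with prostate cancer have preexisting antibody and T-cell responses to PAP", so baselines can be expected to differ. Background subtraction can also leave a baseline at or below zero, where 3-fold is undefined or trivially met, and the plan has no rule for this.

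Regressing such an outcome on the same baseline can yield an apparent finding that pre-existing PAP immunity hinders the vaccine response, even when the vaccine multiplies every patient's frequency equally or does nothing. Section 13 tests these comparisons at two-sided 0.05 without multiplicity adjustment, so the result could be reported as an association.

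**Working it through.** The plan states no figure for D.1 or for the immune-response rate, so there is nothing to reproduce. The size has to be explored under assumptions.

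**Inputs.** From the documents: the 3-fold rule, the media-only criterion, 25 vaccine patients in the biomarker cohort (53 if both cohorts are used), and the 0.05 level. Assumed: log-normal frequencies, median 20, between-patient SD s = 0.8 and assay SD w = 0.4, 0.6 or 0.8 on the natural-log scale, and a split at the median observed baseline.

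**Algebra.** Let u be a patient's true log frequency, B = u + e0 the baseline, P = u + d + e1 the post-treatment value, and d a constant treatment effect. The fold rule is P − B ≥ ln 3. Since P − B = d + e1 − e0, the true level u cancels but e0 remains, with the opposite sign to its sign in B:

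corr(P − B, B) = −w / √[2(s² + w²)]

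- w = 0.4: −0.4/√1.60 = −0.32
- w = 0.6: −0.6/√2.00 = −0.42
- w = 0.8: −0.8/√2.56 = −0.50

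The correlation is negative for any d, including d = 0.

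**Simulated response rates, fold rule alone**

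| Effect | w | High baseline | Low baseline | Odds ratio |
|---|---|---|---|---|
| None | 0.4 | 1.1% | 4.0% | 0.27 |
| None | 0.6 | 4.0% | 15.5% | 0.23 |
| None | 0.8 | 6.6% | 26.4% | 0.20 |
| Doubling | 0.4 | 15.9% | 31.5% | 0.41 |
| Doubling | 0.6 | 19.2% | 44.1% | 0.30 |
| Doubling | 0.8 | 20.4% | 51.5% | 0.24 |

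For example, with w = 0.8 and no effect: (0.066/0.934)/(0.264/0.736) = 0.20.

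**At trial size.** With doubling, a 5% Fisher test on the median split is significant in about 7 to 29% of trials with 25 vaccine patients and 18 to 59% with 53. With no effect and 25 patients, the rates are about 0%, 2% and 11% for the three values of w.

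**Both parts of the rule.** A second model used Poisson ELISPOT wells (assumed background 1 or 5 spots per well, median PAP signal 1 or 3) and called a baseline positive if it differed from media.

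- Post-treatment frequency unrelated to baseline, 8 replicates: odds ratio 0.07 to 0.14.
- Vaccine multiplies baseline (3 or 8 replicates): 0.58 to 1.13 for a 3-fold effect and 0.95 to 1.86 for a 10-fold effect.
- Baseline predictor independent of T-cell frequency (log-normal model, fold rule alone): 1.00.

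**Candidate replacements, first model, no treatment effect.**

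- Slope of P on B = s²/(s² + w²): 0.64/0.80 = 0.80, 0.64/1.00 = 0.64, 0.64/1.28 = 0.50. The main slope is positive with no vaccine effect at all.
- A fixed post-treatment threshold between 20 and 60 gives an odds ratio of about 4 to 64 in favour of high baseline.
- The baseline-by-arm term has no such bias. With doubling in the vaccine arm and no effect in the GM-CSF arm, it rejects in 4 to 6% of trials, which is the nominal level.

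**Precision of the interaction.** With r equal to the slope above and n per arm, SE ≈ √[2(1 − r²)/n]. For n = 25 this is √(0.72/25) = 0.17 to √(1.50/25) = 0.24. For n = 53 it is √(0.72/53) = 0.12 to √(1.50/53) = 0.17.

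**The case against.** Five points can be made for the plan.

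1. **The outcome is inferred.** The plan calls it Th1-biased and nowhere assigns the 3-fold rule to the D.1 regression. That is true. But it is the only T-cell response definition in Section 13, and the Section 11.B.1 criterion also refers back to pre-treatment wells. The point stands unless another outcome is specified.

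2. **The sign is not fixed.** A reader might infer that a negative result is certain. The documents do not support this: the media-only criterion favours patients with higher true frequencies, and the well-level model shows it can cancel or reverse the pull. What remains is an estimate that depends on assay background and replicate number as well as on biology.

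3. **D.1 is not unanswerable.** The tvDTH regulatory measure is not the denominator of the ratio, and MFS involves no ratio. Both are outside this point.

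4. **A constant absolute increment is not an artefact.** If the vaccine added the same number of cells to everyone, the true fold rise would depend on baseline, and a negative association would be real on that scale. That case is not used as evidence here.

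5. **D.1 is exploratory.** No section says its result will select patients for later trials. Exploratory status excuses low power and unadjusted testing. It does not excuse an outcome that can create an association by arithmetic.

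**Conclusion.** The coupling is real but limited to the T-cell predictors in D.1. It pulls the planned logistic regression in the negative direction: odds ratios of 0.20 to 0.27 with no effect and 0.24 to 0.41 under uniform doubling, with no dependence of the fold effect on baseline. These figures apply the fold rule alone and rest on assumed SDs, log-normality and a median split. The plan speaks of the presence of a baseline response, which may mean a different cut.

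A reader might extend the point to the immune-response comparison between arms or to the primary endpoint. Neither follows: randomisation makes the coupling the same in both arms under no effect, and the primary MFS analysis does not use these assays. This is a change worth making before unblinding, not a threat to the trial's main conclusions.

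**What to change.** For the T-cell part of D.1, name the outcome as log post-treatment PAP-specific frequency, floored at a stated assay detection limit, which also settles zero and negative values. Apply the same floor to baseline. Regress the outcome on baseline log frequency, arm and baseline-by-arm, using both arms. Base the D.1 conclusion on the baseline-by-arm term only, read as whether the vaccine's fold effect varies with baseline. State that neither the main baseline slope nor a fixed post-treatment threshold will be read as prediction, because persistence and regression to the mean make both positive without any vaccine effect. Keep the 3-fold rule for the between-arm response-rate comparison.

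The cost is SAP wording: the immune blood draws are already scheduled in both arms. There are two downsides. D.1 is worded for vaccine recipients and would no longer be expressed in 3-fold responders. The interaction is also imprecise: from the standard errors above, the 95% half-width is about 1.96 × 0.17 = 0.33 to 1.96 × 0.24 = 0.47 with 25 per arm, and 1.96 × 0.12 = 0.24 to 1.96 × 0.17 = 0.33 with 53. It should be reported as an estimate with its interval.
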